5.1 Descriptive analyses

Due to a limited PK sampling, only summary statistics of measured PK concentrations will be reported, and no further PK parameters will be determined for this study.

LNA043 and ANGPTL3 serum and synovial fluid concentration data will be listed by subject, and visit/sampling time point, separately for each study part. Descriptive summary statistics will be provided by treatment, study part and visit/sampling time point, including

Commercially Confidential Information

Summary statistics will include mean (arithmetic and geometric), Standard Deviation (SD), CV (arithmetic and geometric), median, minimum and maximum.

The PK analysis will be done separately for part A and part B.

6 Statistical methods for Pharmacodynamic (PD) parameters

All subjects within the PD analysis set will be included in the efficacy PD data analysis, unless otherwise stated. For MRI related assessments, all subjects within the PD analysis set and subjects who completed Week 28 and/or Week 52, for Part B will be included.

6.1 Primary objective

The primary objective of this study related to efficacy is to assess the efficacy of multiple i.a. injections of LNA043 in regenerating the articular cartilage tissue.

6.1.1 Variables

The primary efficacy variables are:

- The change from baseline in **articular cartilage bi-layer collagen organization from T2 relaxation rates** in superficial and deep cartilage layers measurements, and overall, will be evaluated with MRI at baseline, Weeks 8, 16 and 28 from both lesions (femoral condyle and patella) for **Part A**.

Baseline for bi-layer collagen organization is defined as Visit 1 (Day -35 to -5) from Part A.

- The change from baseline in **cartilage volume in the index region**, assessed based on MRI at Weeks 28 and 52 (**Part B**). The index region is defined as being a combination of 3 sub-regions, i.e. the femur medial anterior (FMA), femur medial central (FMC) and femur medial posterior (FMP).

The **cartilage volume in index region** is defined as the summation of the three subcategories, i.e.:

Cartilage volume in index region (mm³) = FMA volume + FMC volume + FMP volume

Baseline for the cartilage volume is defined as Visit 1 (Day -35 to -5) from Part B.

- The change from baseline in **cartilage thickness in the index region**, assessed based on MRI at Weeks 28 and 52 (**Part B**). The index region is defined on the above bulletpoint.

The **cartilage thickness in index region** is defined as the mean of the three subcategories, i.e.:

Cartilage thickness in index region (micrometer) = (FMA thickness + FMC thickness + FMP thickness)/3

Baseline for the cartilage thickness is defined as Visit 1 (Day -35 to -5) from Part B.

6.1.2 Descriptive analyses

The articular cartilage bi-layer collagen organization (Part A) will be listed by treatment group, patient, visit/time, cartilage layer (deep, superficial and overall) and lesion type (femoral condyles, patella) and region. Summary statistics will be provided for both layer (and overall), lesion type (and overall), regions and their difference by treatment group and visit/time.

Similarly, for the cartilage volume and cartilage thickness in the index region (Part B), will be listed separately by treatment group, patient and visit/time. Summary statistics will be provided by treatment group and visit/time.

For primary endpoints, summary statistics will include mean (arithmetic), SD, CV, median, minimum, maximum and graphical methods will be employed for each endpoint to show group and individual summary plots over time by treatment group, visit/time, layer (and overall), lesion type (and overall), and regions, if applicable depending on study Part. Lesion type and region is only applicable from Part A endpoints.

Additional summary statistics, boxplots and individual plots on raw data for cartilage volume in index region and in sub-regions of the knee cartilage, may be employed based on Population B, defined in Section 6, whereas boxplots and individual plots for change from baseline of cartilage volume may be employed based on Population Aa. Moreover, data based on Population B will be only summarized for cartilage thickness in the index region and in sub-regions of the knee cartilages

6.1.3 Statistical model, assumptions and hypotheses

6.1.3.1 Part A

The primary efficacy variable for Part A, change from baseline in articular cartilage bi-layer collagen organization will be analyzed using a mixed effect model for repeated measures (MMRM) analysis of variance model for each layer (deep and superficial) separately and for both layers combined, and region; including all-time points to compare treatment groups at Weeks 16 and 28. The model will include baseline as a covariate, treatment, timepoint, treatment*timepoint and type of lesion as fixed effects and subject as a random effect.

A two-sided 90% confidence intervals for the treatment effect will be formed at Weeks 8, 16 and 28. Considering that the time course of response to LNA043 is not known, statistically significant differences (one-sided p-value of treatment superiority to placebo at 95% significance level) between active drug and placebo at either Week 16 or Week 28 will be considered as a positive result.

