11.4.2.1 Part A

The primary efficacy variable, articular cartilage bi-layer collagen organization, assessed based on MRI at Weeks cc116 and 28, will be analyzed using a mixed model repeated measures (MMRM) analysis of variance model, including baseline and all time points to compare treatment groups at Weeks CCI16 and Week 28. The model will include treatment, timepoint, treatment*timepoint, and type of lesion as fixed effects, subject as a random effect, and baseline measure as a fixed covariate. If deemed appropriate, the endpoint measure data will be transformed to facilitate analysis. 90% two-sided confidence intervals for the treatment effect will be formed at Weeks CCI16 and Week 28. Considering that the time course of response to LNA043 is not known, statistically significant differences between active drug and placebo at either Week 16 or Week 28 will be considered as a positive result.

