11.9 Sample size calculation

11.9.1 Part A

Commercially Confidential Information

A sample size of 36 LNA043 treated patients and 12 Placebo patients (48 patients, 3:1 LNA043:Placebo) will allow for approximately 90% power, with a 1-sided alpha of 0.05, to detect a 20% relative difference between LNA043 and Placebo overall, and CCI . Stated differently, a two-sided 90% confidence interval for the treatment effect will exclude zero with probability 90%.

A 20% relative improvement in T2 mapping between treatments is considered to be potentially clinically meaningful and statistically different than the 10% random variability. So, in the calculations above, an effect size of 0.2/0.18=1.11 is used.

Page 95 Protocol No. CLNA043X2202

Commercially Confidential Information

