6.1.3.2 Part B

The primary efficacy variable for Part B, change from baseline in cartilage volume in the index region will be analyzed using a mixed effect model for repeated measures (MMRM) analysis of variance model, including all-time points to compare treatment groups at Weeks 28 and 52. The model will include baseline as a covariate, treatment, timepoint, treatment*timepoint as fixed effects. An unstructured covariance will be assumed; if not possible, other appropriate covariance structures will be explored such as Autoregressive (AR(1)), Compound symmetry, etc.

The change from baseline in cartilage thickness in the index region will be similarly analyzed using the MMRM described above for the change from baseline in cartilage volume in the index region.

A two-sided 90% confidence intervals for the treatment effect will be formed at Weeks 28 and 52. Considering that the time course of response to LNA043 is not known, statistically significant differences (one-sided p-value of treatment superiority to placebo at 95% significance level) between active drug (either LNA043 dose) and placebo at either Week 28 or Week 52 will be considered as a positive result. No multiplicity adjustment will be considered. If deemed appropriate, the endpoint measure data will be transformed to facilitate analysis.

Same analyses (table and figures) for the MMRM models of change from baseline in cartilage volume in the index region as well as for the change from baseline in the cartilage thickness in the index region may be implemented based on the Population A, defined in Section 6.

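### The Part A MMRM carries only a random subject effect, which with default residuals assumes equal variance at Weeks 8, 16 and 28; it should use the unstructured covariance that the SAP adopts for Part B

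*SAP*

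**What the plan says.** For Part A, SAP 6.1.3.1 fits baseline, treatment, timepoint, "treatment*timepoint and type of lesion as fixed effects and subject as a random effect". Protocol 11.4.2.1 agrees: "fixed effects, subject as a random effect, and baseline measure as a fixed covariate". Neither section names a residual covariance structure, a robust standard error or a fallback.

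The outcome "will be evaluated with MRI at baseline, Weeks 8, 16 and 28" (SAP 6.1.1), so three post-baseline visits enter the model. On inference, SAP 6.1.3.1 says "A two-sided 90% confidence intervals for the treatment effect will be formed at Weeks 8, 16 and 28". Its success rule is that a significant difference "between active drug and placebo at either Week 16 or Week 28 will be considered as a positive result". Week 8 therefore contributes data but is not a decision visit. Separate models are fitted by layer, for both layers combined, and by region. SAP 6.2.3.1 carries a similar model to defect-filling volume, and protocol 11.7 specifies the same random subject effect for that endpoint.

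For Part B, protocol 11.4.2.2 also lists the participant as a random effect, but SAP 6.1.3.2 drops that term: "An unstructured covariance will be assumed; if not possible, other appropriate covariance structures will be explored". AR(1) and compound symmetry are named there as examples of fallbacks.

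**The concern.** A random subject intercept with independent residuals is compound symmetry. Each visit then has the same variance, and each pair of visits the same correlation. The Week 28 comparison is judged against a variance averaged over all three visits, including Week 8.

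Either Week 16 or Week 28 alone can declare Part A positive, so the Week 28 standard error bears directly on that call. Both documents say that the time course of response is unknown, and neither gives a reason to expect constant variability. If the spread of the change from baseline grows with follow-up, the Week 28 interval is too narrow and its one-sided error exceeds 5%. If the spread shrinks, the interval is too wide and power is lost. The same SAP already avoids this assumption in Part B and does not say why Part A differs.

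**Working it through.** **Inputs from the documents.** Visits at Weeks 8, 16 and 28; two-sided 90% intervals, equivalent to one-sided 5% tests; 36 LNA043 and 12 placebo completers (protocol 11.9.1); 20% dropout, 60 × 0.8 = 48 (protocol section 4). The only SD visible is 0.18, not split by visit.

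**The plan's own figure.** Protocol 11.9.1 says of these numbers that they "will allow for approximately 90% power, with a 1-sided alpha of 0.05". With effect size 0.2/0.18 = 1.111, the noncentrality is 1.111 / √(1/36 + 1/12) = 3.333. Power is Φ(3.333 − 1.645) = 95.4% (94.9% with the t distribution). About 90% appears only at one-sided 0.025 (91.5% normal, 90.4% t). The stated 90% is thus conservative for its own inputs, and the surrounding text is partly redacted. This is a separate matter, and nothing below depends on it.

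**Closed form.** With complete data, and treating variances as known:

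- SE ratio at Week 28: r = √(mean of the three visit variances / Week 28 variance)
- One-sided error: 1 − Φ(1.645 r)

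For SDs 0.9/1.0/1.1: mean variance (0.81 + 1.00 + 1.21)/3 = 1.0067; r = √(1.0067/1.21) = 0.912; error 1 − Φ(1.500) = 6.7%.

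The SDs below are assumptions, since the documents give none.

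| SD at Weeks 8/16/28 | r at Week 28 | One-sided error, Week 28 | One-sided error, Week 16 |
|---|---|---|---|
| 1.0/1.0/1.0 | 1.000 | 5.0% | 5.0% |
| 0.9/1.0/1.1 | 0.912 | 6.7% | 4.9% |
| 0.85/1.0/1.15 | 0.876 | 7.5% | 4.9% |
| 0.7/1.0/1.3 | 0.792 | 9.6% | 4.5% |
| 1.15/1.0/0.85 | 1.185 | 2.6% | 4.9% |

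Simulation of the three rising patterns and the falling one (36:12, correlation 0.6) gave 6.4%, 7.2%, 10% and 2.4% at Week 28.

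**Check with fitted models.** REML random-intercept fits used 4,000 trials per scenario, an assumed correlation of 0.5, baseline and lesion type in the model, and a second set of SD ratios. Coverage of the Week 28 90% interval was:

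| SD ratio, Weeks 8:16:28 | 36:12, complete data | 45:15, 20% dropout |
|---|---|---|
| 1:1:1 | 0.906 | 0.902 |
| 1:1.1:1.25 | 0.859 | 0.858 |
| 1:1.25:1.5 | 0.846 | 0.842 |
| 1:1.5:2 | 0.803 | 0.793 |
| 1:0.8:0.67 | 0.958 | 0.961 |

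A Week 28 ANCOVA with its own variance, standing in for the unstructured model, covered 0.89 to 0.91 throughout.

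**Effect on the either-visit rule** (36:12, correlation 0.6, complete data, 40,000 null trials). The chance of a positive result under the random-intercept model, against visit-specific variances, was about 8.4% v 8.4% with equal SDs, 9.7% v 8.3% for 0.9/1.0/1.1, 10.2% v 8.3% for 0.85/1.0/1.15, 12% v 8.4% for 0.7/1.0/1.3, and 6.4% v 8.1% for the falling pattern.

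**The case against.** The strongest reply is that the SAP does not say compound symmetry. It names a random subject effect, calls the model an MMRM, and is silent on the residuals. Protocol 11.4.2.2 uses the same random-effect language for Part B, yet the SAP implements that as unstructured, so in this sponsor's usage the phrase may not imply equal variance. This stands in part. A reader might infer that the plan deliberately forces equal variance on Part A; the documents do not support that. What they support is that the model, read literally with default residuals, makes the assumption, and that Part B received the correction while Part A did not.

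A reader might also infer that the Week 28 interval is wrong. No visit SD is given, the direction of any drift is unknown, and the 10% figure needs the SD to rise by 86% (0.7 to 1.3). Nor is that figure the error of the whole decision: the either-visit rule already runs at about 8.4% with equal SDs, and mild or moderate drift adds one to two points.

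With about 12 placebo completers and several models by layer and region, a parsimonious structure is arguable. But six covariance parameters are manageable with 48 patients, and the cost is small. SAP 6.1.4 and parts of protocol 11.5 are redacted and could contain a covariance sensitivity analysis. The SAP section is headed as supportive, however, and the Part A model paragraph itself shows no redaction.

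**Conclusion.** The point holds conditionally. As written and with default independent residuals, the Part A primary and secondary models assume equal variance and equal correlation at Weeks 8, 16 and 28. Under assumed SDs that rise modestly to strongly, the Week 28 standard error is about 9% to 21% too small, and its one-sided error about 6.5% to 10%. Under an assumed fall, the error is about 2.5% and the interval too wide. Equal SDs give no error. The Week 16 interval stays close to nominal in the scenarios tried.

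These sizes rest on assumed SD ratios, with correlations of 0.5 or 0.6 in the simulations; they are not estimates for this trial. The study is non-confirmatory, so this should be changed but does not invalidate the design. The reason to act is that a safer specification already stands in the same SAP and costs little.

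**What to change.** In SAP 6.1.3.1, replace the random subject effect with the Part B specification: an unstructured covariance across Weeks 8, 16 and 28, with small-sample degrees of freedom (for example Kenward-Roger) and a fallback order stated in advance. Structures that keep visit-specific variances should come first in that order, because standard AR(1) and compound symmetry bring back the equal-variance assumption. State that SAP 6.2.3.1 follows.

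Protocol 11.4.2.1 and 11.7 carry the random-effect wording, so record the change in the SAP as a departure from them. Protocol 3.2.2 already describes Part A results as positive, and protocol 6.4 allows treatment assignments to be used for interim analyses. If Part A outcomes have been seen unblinded, document when the change was made and who had seen the data, and report the random-intercept model alongside.

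The cost is a short SAP edit and six covariance parameters instead of two. If variances are in fact equal, error degrees of freedom fall from about 82 to 46 (assumed correlation 0.6, complete data). The 90% interval then widens by about 1% (t quantile 1.679 against 1.664). A baseline-by-timepoint term is optional and not part of this point.

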6.1.3.2 Part B

The primary efficacy variable for Part B, change from baseline in cartilage volume in the index region will be analyzed using a mixed effect model for repeated measures (MMRM) analysis of variance model, including all-time points to compare treatment groups at Weeks 28 and 52. The model will include baseline as a covariate, treatment, timepoint, treatment*timepoint as fixed effects. An unstructured covariance will be assumed; if not possible, other appropriate covariance structures will be explored such as Autoregressive (AR(1)), Compound symmetry, etc.

The change from baseline in cartilage thickness in the index region will be similarly analyzed using the MMRM described above for the change from baseline in cartilage volume in the index region.

A two-sided 90% confidence intervals for the treatment effect will be formed at Weeks 28 and 52. Considering that the time course of response to LNA043 is not known, statistically significant differences (one-sided p-value of treatment superiority to placebo at 95% significance level) between active drug (either LNA043 dose) and placebo at either Week 28 or Week 52 will be considered as a positive result. No multiplicity adjustment will be considered. If deemed appropriate, the endpoint measure data will be transformed to facilitate analysis.

Same analyses (table and figures) for the MMRM models of change from baseline in cartilage volume in the index region as well as for the change from baseline in the cartilage thickness in the index region may be implemented based on the Population A, defined in Section 6.

6.1.4 Supportive analysis

Commercially Confidential Information

6.2 Secondary objectives

6.2.1 Variables

The secondary variables are:

- Change from baseline in **volume of cartilage defect filling** (mm³) assessed based on MRI at Weeks 8, Weeks 16 and 28 (**Part A**).

Baseline for volume of cartilage defect filling (mm³) is defined as Visit 1 (Days -35 to -5).

- Change from baseline in articular cartilage bi-layer collagen organization, evaluated with T2 relaxation times measured in superficial and deep layers of the index region by T2 mapping MRI at Week 28 and 52 (**Part B**).

The **cartilage T2 in index region** is defined as the mean of the three subcategories, i.e.:

Cartilage mean T2 in index region (ms) = (FMA T2 + FMC T2 + FMP T2)/3.

Baseline for bi-layer collagen organization is defined as Visit 1 (Day -35 to -5).

6.2.2 Descriptive analyses

The volume of cartilage defect filling variable (Part A) will be listed by treatment group, patient, visit/time, region and lesion type. Summary statistics will be provided by treatment group, visit/time and lesion type (femoral condyle, patella and overall).

The articular cartilage bi-layer collagen organization (Part B) will be listed by treatment group, patient, visit/time, cartilage layer (deep, middle, superficial and overall). Summary statistics will be provided for all layers (and overall) and their difference by treatment group and visit/time.

For both secondary endpoints, summary statistics will include mean (arithmetic), SD, CV, median, minimum, maximum and graphical methods will be employed for each endpoint, to show group and individual summary plots over time by treatment, lesion type (and overall) and layer (and overall), if applicable depending on study Part. Lesion type is only applicable from Part A endpoint.

Other secondary efficacy variables will be summarized graphically and in summary tables.

6.2.3 Statistical model, assumptions and hypotheses

6.2.3.1 Part A

Change from baseline in volume of cartilage defect filling (mm³) will be analyzed at Weeks 16 and 28 using similar MMRM and confidence intervals for the treatment effect as described in Section 6.1.3.1. A single MMRM model will be used, since there are no layers for this secondary endpoint.

6.2.3.2 Part B

Change from baseline in articular cartilage bi-layer collagen organization, assessed based on MRI, will be analyzed at Weeks 28 and 52, using a similar MMRM and confidence intervals for the treatment effect as described in Section 6.1.3.2, where layer categories are deep, middle and superficial.

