2.2 Secondary objective(s)

Secondary objective(s)	Endpoints related to secondary objective(s)		
To assess the extent of the repair cartilage tissue following multiple i.a. injections of LNA043	 Change in volume of cartilage defect filling evaluated with MRI at Week 16 and 28 (Part A) Articular cartilage bi-layer collagen organization evaluated with T2 relaxation times measured in superficial and deep layers by T2 mapping Magnetic Resonance Imaging (MRI) at Week 28 and 52 (Part B) 		
To evaluate systemic and local PK of LNA043 following multiple i.a. injections of LNA043	Serum and synovial fluid PK profile of LNA043 and ANGPTL3		
To assess the potential immunogenicity of LNA043	Presence and characterization of anti- LNA043 antibodies in serum at Day 1, Day 15, Day 50, Day 106 and Day 190 (Part A) and Day 1, Day 29, Day 57, Day 85, Day 113, Day 197 and Day 365 (Part B)		

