3.2.2 Part B

- Based on the positive results of the CLNA043X2201 study and of this ongoing CLNA043X2202 study (Part A), a broader patient population of knee OA with high medical need patient population is now being evaluated in part B.
- The patient population of knee OA K&L 2-3 with JSW 2.00-4.00mm has been selected based on the post-hoc analysis of the FORWARD trial (Gühring et al 2019),

- The MRI data collected at different time points will allow for the evaluation of the short-and long-term effect of one monthly cycle of i.a. treatment with LNA043 and a comparison between the 2 doses tested (20 mg and 40 mg). Meanwhile, since the image analysis will cover well-defined regions the articular cartilage throughout the knee as has been done in part A, results from part B, especially those obtained from the 20 mg group, may also be compared with the results from part A to evaluate the potential added benefit of the monthly dosing regimen in the index region (as defined in part B) vs the damaged region (as defined in part A).
- The monthly dosing regimen (x 4) has been selected based on the results of the FIH clinical study, which suggests a long PD effect of LNA043.

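### The SAP models the Part B secondary T2 endpoint on three cartilage layers although it is defined on two, so an undefined middle layer can count towards a positive result

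*SAP*

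**What the plan says.** The endpoint is defined on two layers. Protocol 2.2 gives it as "Articular cartilage bi-layer collagen organization evaluated with T2 relaxation times measured in superficial and deep layers" at Weeks 28 and 52 in Part B. SAP 1.3.2 repeats this. SAP 6.2.1 defines the variable as change from baseline, "evaluated with T2 relaxation times measured in superficial and deep layers of the index region by T2 mapping MRI".

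The analysis uses three. SAP 6.2.2 lists Part B T2 by "cartilage layer (deep, middle, superficial and overall", and summarises all layers together with their difference. SAP 6.2.3.2 calls for an MMRM similar to that of SAP 6.1.3.2, "where layer categories are deep, middle and superficial".

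Part A stays with two. SAP 6.1.3.1 fits the model "for each layer (deep and superficial) separately and for both layers combined".

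Three further statements matter:

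- Protocol 11.7 treats a significant difference from placebo for either dose, at Week 28 or Week 52, as a positive result for this endpoint. It does not mention layers.
- SAP 6.1.3.2, the section to which 6.2.3.2 refers, rules out multiplicity adjustment.
- Protocol 3.2.2 says that "results from part B, especially those obtained from the 20 mg group, may also be compared with the results from part A", to look at the monthly regimen.

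**The concern.** The variable definition and the analysis sections disagree on what is analysed. The middle layer has no boundary and no stated rationale, and nothing labels it supportive. It appears in both SAP 6.2.2 and 6.2.3.2, so it is unlikely to be a slip.

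Two things are at stake. First, the success rule is silent on layers, so a middle-layer difference alone could be reported as a positive secondary finding although the endpoint does not include that layer. Second, if two layers span the cartilage depth, a third must be cut out of one or both of them. Superficial and deep could then describe different tissue from the protocol endpoint, and from the layers of the same name in Part A.

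There is also a smaller gap. With two layers the layer difference is one quantity. With three there are three pairwise differences, and SAP 6.2.2 does not say which is meant.

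**Working it through.** The documents state no figure on this point that could be reproduced, and the Part B sample-size text is redacted. The check is a comparison of the texts plus two illustrations.

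**Step 1. Layer sets side by side.**

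| Place | Layers |
|---|---|
| Protocol 2.2, Part B endpoint | superficial, deep |
| SAP 1.3.2 and 6.2.1, Part B variable | superficial, deep |
| SAP 6.2.2, Part B summaries | deep, middle, superficial, overall |
| SAP 6.2.3.2, Part B model | deep, middle, superficial |
| SAP 6.1.2, Part A summaries | deep, superficial, overall |
| SAP 6.1.3.1, Part A model | deep, superficial, combined |

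Protocol 8.5.1 describes hyaline cartilage as having two main layers between surface and bone. It leaves acquisition and analysis details to an imaging charter.

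**Step 2. Number of comparisons.** Inputs: 2 active doses against placebo and 2 weeks (Protocol 11.7). Assumption: one model per layer, as Part A does. SAP 6.1.3.2 has no layer term, so the documents do not settle this.

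- Two layers: 2 × 2 × 2 = 8.
- Three layers: 2 × 2 × 3 = 12.
- If an overall value is also modelled: 12 with two layers, 16 with three.

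**Step 3. Chance of at least one false positive.** With k independent tests at one-sided 0.05 (SAP 6.1.3.2) and no true effect, it is 1 − 0.95^k.

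- k = 8: 33.7%.
- k = 12: 46.0%.
- k = 16: 56.0%.

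The tests share a placebo arm, the same patients at two weeks and the same cartilage, so they are correlated and the true values are lower. The documents give no correlations from which to say by how much.

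**Step 4. Could the superficial treatment effect itself change?** Let d run from 0 at the bone to 1 at the surface, and assume layers of equal thickness. With two layers, superficial is the mean effect over d from 1/2 to 1. With three, it is the mean over d from 2/3 to 1.

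| Assumed effect over depth | Two layers | Three layers | Ratio |
|---|---|---|---|
| Uniform | 1.000 | 1.000 | 1.00 |
| Rising linearly to the surface | 0.750 | 0.833 | 1.11 |
| Top third only | (1/3)/(1/2) = 0.667 | 1.000 | 1.50 |

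These three profiles are not bounds. An effect falling linearly from bone to surface gives means of 0.250 and 0.167, a ratio of 0.167/0.250 = 0.67. The partition may therefore matter or not, and without boundaries and a depth profile its size cannot be fixed.

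**The case against.** The strongest reply is that this is a wording mismatch in a secondary endpoint of a study labelled non-confirmatory. Superficial and deep are still modelled. Within Part B every arm is measured with the same partition, so a third layer creates no spurious treatment effect. The extra comparisons sit in a plan that openly declines multiplicity control. All of that stands, and it limits the weight of the point. It does not answer which layers carry the endpoint or the success rule.

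A reader might go further and infer three things that the documents do not support.

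- *That Part B superficial and deep values do differ from the two-layer ones.* The boundaries are in the imaging charter, which is not among the documents. Modelling both layers combined in Part A makes it plausible that the two fill the full depth, but does not prove it.
- *That Part B cannot be compared with Part A as the protocol intends.* Protocol 3.2.2 is permissive, names no T2 layer, and already accepts different regions (index region against damaged region). Overall T2 stays comparable in this respect if it is a full-depth mean in both parts. With an assumed linear profile from 30 ms at bone to 50 ms at the surface, that mean is 40.0 ms however the layers are cut.
- *That the superficial-minus-deep contrast is 33% larger in Part B.* On the same assumed profile, halves give 45.0 − 35.0 = 10.0 ms and thirds 46.7 − 33.3 = 13.3 ms, a ratio of 1.33. This needs linearity and equal layers. It also concerns a descriptive contrast of T2 levels, not the modelled change from baseline against placebo.

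**Conclusion.** The SAP is wrong as written. Its Part B T2 analysis departs from Protocol 2.2 and from its own section 6.2.1 by adding a layer that it does not define. No primary or secondary endpoint names that layer; the exploratory endpoints are redacted, so nothing can be said about those.

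The firm consequence is four extra chances of a positive secondary result, 12 comparisons instead of 8, if layers are modelled separately. Under independence that moves the chance of at least one false positive from 33.7% to 46.0%, which overstates the level of both because the tests are correlated.

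The second consequence is a gap in the evidence. Layer-specific T2 in Part B is not shown to match the protocol endpoint or Part A's layers. With equal layers assumed, the superficial effect ratio runs from 1.00 to 1.50 over the three main profiles tried. The documents support neither a fixed size for this mismatch nor a claim that the two parts cannot be compared.

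**What to change.** - **SAP 6.2.3.2:** limit the secondary MMRM and the positive-result rule to the superficial and deep layers of 6.2.1, using Part A's two-layer boundaries where the existing T2 maps allow. Say whether each layer has its own model and whether overall T2 is modelled.
- **SAP 6.2.2:** define each layer and the overall value, report the middle layer as descriptive only, and state that the layer difference is superficial minus deep.
- **If Part A's boundaries cannot be applied:** state that layer-level T2 will not be compared between Parts A and B, and use overall full-depth T2 for any such comparison. This fallback controls what may be declared positive. It does not restore a two-layer measurement, so the boundaries used should be stated.

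The cost is SAP wording and, where feasible, a re-partition of existing maps by the central imaging reviewers, with no new scans. The documents do not show whether re-partition is feasible, so it should not be a condition of the change. The downside is that some depth detail moves from modelled to descriptive.
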